Statistical Power & Analyses. The approach to the analysis will utilize repeated measures mixed model analysis of covariance. For simplicity of exposition, this is described with the outcome not as a vector of 4 measurements, but instead as the analysis of a series of one-dimensional difference scores, with each difference score taken relative to the baseline measurement. Model covariates will include baseline score, variables unexpectedly unbalanced between groups at baseline (i.e., to account for potential bias), and variables that may be correlated with the outcome (i.e., to increase precision). Potential covariates include depression, social support, physical activity, medical/demographic variables including cancer treatments, and recruitment site.

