imposed by study design and sample size) with an intervention having this level of efficacy.¹ In an unadjusted analysis, the effect size equals the difference between the group means divided by the pooled standard deviation. (Consistent with previous data, this could for example be a difference in mean pain scores of 5.0 vs 4.0; SD= 2.0). Such a power calculation is conservative, as the reduction in degrees of freedom associated with the covariates in an adjusted analysis should have less of an impact than the reduction in the mean squared error associated with those same covariates.

Aim 2: Explore potential mediators (i.e., self-efficacy for pain control, pain catastrophizing) through which mPCST-Community leads to reduction in pain severity, pain interference, fatigue, physical disability, and psychological disability. This hypothesis will be explored, for example, by first fitting a model with intervention group as the primary predictor and self-efficacy as an outcome, and then by fitting a second model with self-efficacy as the primary predictor and pain severity as an outcome. Including intervention group in this latter model also allows us to test an interaction between self-efficacy and intervention group and, thus, assess whether the relationship between self-efficacy and pain severity is consistent across study groups. In contradistinction with the other analyses associated with this aim, the test for interaction is likely to have modest power and thus is considered to be exploratory. The same caveat applies to other interactions – for example, for aim 1 a test of whether the impact of the intervention is consistent across gender or other similarly-defined patient subgroup. This approach to mediator analyses is appropriate given the relative lack of maturity of the science examining interactions within behavioral intervention trials; while this study is designed around main effects, Aim 2 provides adequate new knowledge within the practical constraints of this trial. This approach to mediation analyses is consistent with current analysis of RCTs from the biomedical literature.¹³⁴⁻¹³⁶

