Aim 3: To evaluate cost, cost-effectiveness and practicality of mPCST-Community. **Analyses.** We will use patient-level data to test for differences between mPCST-Community and the Health-Edu conditions on medical resource use, medical costs and productivity costs. We will use generalized linear models specified using negative binomial error distributions and log links for resource use and gamma error distributions and log links for costs. We will apply mixed-effects linear regression models to test for interactions between study interventions and time on EQ-5D-derived preference weights across the 6-month follow-up period. Baseline resource use and EQ-5D weights will be included as covariates in regression models. For each patient will compute quality-adjusted life-years (QALY) using the trapezoidal rule applied to EQ-5D weights at baseline, post-intervention, 3 months and 6 months. Because the mHealth-Ed control was designed to control for patient contact time and does not represent standard care, accounting for the costs of providing this condition and patient time spent participating would inappropriately offset the costs associated with the mPCST-Community intervention. Therefore, we will modify our calculation of the numerator of incremental cost-effectiveness ratio (ICER) in which we will calculate the difference in mean medical costs and productivity costs between the mPCST-Community and mHealth-Ed control groups then add direct costs of resources required to provide mPCST-Community as well as participant time costs. To compute the difference in QALYs, we will subtract mean QALYs in the mHealth-Ed condition from mean QALYs in the mPCST-Community condition. Then, we will divide the estimated difference in mean costs by the difference in mean QALYs and generate a 95% confidence interval constructed using nonparametric bootstrapping. We then will calculate net health benefits (QALY* λ – Cost, where λ represents maximum willingness to pay per QALY) for each patient, and apply linear regression analysis to evaluate whether intervention and patient baseline characteristics are associated with improved cost-effectiveness. In sensitivity analyses, we will evaluate the impact of: (1) applying various durations of sustained benefit beyond the 6-month follow-up period; (2) excluding productivity gains/costs; and (3) assuming patients could participate in videoconferencing at home. To evaluate practicality and sustainability of PCST-Community, we will assess accrual, participant retention, and intervention protocol adherence.

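### The Aim 3 ICER divides by an unadjusted difference in mean QALYs, although baseline EQ-5D is collected and is already a planned covariate (minor; a free improvement)

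*Combined protocol and SAP*

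**What the plan says.** All of this is in the combined protocol and SAP, under Data Analysis & Statistical Considerations.

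- Aim 3, QALYs: each patient's QALY comes from the "trapezoidal rule applied to EQ-5D weights at baseline, post-intervention, 3 months and 6 months".
- Aim 3, covariates: "Baseline resource use and EQ-5D weights will be included as covariates in regression models". This follows the sentences on the generalised linear models and the mixed model.
- Aim 3, ICER denominator: "we will subtract mean QALYs in the mHealth-Ed condition from mean QALYs in the mPCST-Community condition".
- Aim 3, ICER: the analysts will "divide the estimated difference in mean costs by the difference in mean QALYs and generate a 95% confidence interval constructed using nonparametric bootstrapping". The bootstrap interval type is not stated, and there is no rule for resamples with a QALY difference at or below zero.
- Aim 3, net benefit: a per-patient net benefit is then computed, and the analysts will "apply linear regression analysis to evaluate whether intervention and patient baseline characteristics are associated with improved cost-effectiveness". No value or range of λ is given, and the baseline characteristics are not listed.
- Statistical Power & Analyses, for the outcome models: "Model covariates will include baseline score, variables unexpectedly unbalanced between groups at baseline". The Aim 1 power text justifies this on precision: the lost degrees of freedom from "covariates in an adjusted analysis should have less of an impact than the reduction in the mean squared error" those covariates bring.

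**The concern.** The baseline EQ-5D weight enters each QALY directly as the first trapezoid point, and indirectly because patients with better utility at baseline tend to have better utility later. A chance difference between arms at baseline therefore passes into the raw QALY difference and from there into the ICER. For its outcome models the plan removes this kind of noise by adjusting for the baseline score; the ICER denominator is left as a subtraction of means.

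A second, smaller matter concerns the ratio. If the resampled QALY differences fall on both sides of zero, a negative ratio can mean either cheaper and better or dearer and worse. Limits placed on the ratio then do not describe a range of cost per QALY. Since the Aim 3 hypothesis is worded as incremental cost per QALY, a reader may go to that interval first.

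**Working it through.** **The plan's own figure.** The documents give no power or precision figure for Aim 3. The only one is for Aim 1: 72 per group, 80% power, effect size about 0.48. A two-sample t-test with two-sided alpha 0.05 (alpha assumed) gives 81.6% power at 0.48, so that statement reproduces. I take 72 per arm from it.

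**Assumptions not in the documents.** EQ-5D SD 0.20 at every visit. Visit correlation r from 0.3 to 0.7, either equal for all pairs of visits or decaying with the number of visits apart. Low values are included because entry requires pain of at least 4, which may narrow the baseline range. Visits at weeks 0/8/21/34, or at 0/4/17/30 if weekly sessions finish in 4 weeks.

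**Step 1: trapezoid weights w (years).**
- Weeks 0/8/21/34: 4/52 = 0.077, 10.5/52 = 0.202, 13/52 = 0.250, 6.5/52 = 0.125.
- Weeks 0/4/17/30: 0.038, 0.163, 0.250, 0.125.

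**Step 2: variance removed by baseline adjustment.** With visit correlation matrix R, let c be the baseline element of Rw. The proportional variance cut is c²/(w′Rw), and the SE cut is 1 − √(1 − variance cut).

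| Timing | Structure | Variance cut, r = 0.3 / 0.5 / 0.7 |
|---|---|---|
| 8 weeks | equal | 29% / 48% / 69% |
| 8 weeks | decaying | 14% / 27% / 47% |
| 4 weeks | equal | 23% / 43% / 65% |
| 4 weeks | decaying | 8% / 20% / 41% |

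At the extremes, 1 − √(1 − 0.081) = 4% and 1 − √(1 − 0.686) = 44%. In absolute terms the SE falls from 0.0133 to 0.0127 QALY at the low end and from 0.0193 to 0.0108 at the high end. A simulation of 12 scenarios (500 trials each) gave variance cuts of 6 to 72%, in agreement.

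**Step 3: effect of a chance baseline gap.** One SE of the baseline difference is 0.20 × √(2/72) = 0.033. The shift in the raw QALY difference is c × 0.033, with c from 0.113 to 0.481, giving 0.004 to 0.016 QALY. For scale, a sustained 0.3 SD gain (0.06) is worth 0.06 × 0.538 = 0.032 to 0.06 × 0.577 = 0.035 QALY, where 0.538 and 0.577 are the sums of the post-baseline weights.

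**Step 4: how often the 95% interval for the QALY difference contains zero.** This is P(|Z| < 1.96), with Z centred at the true difference divided by its SE.

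| True EQ-5D effect | Raw | Adjusted |
|---|---|---|
| 0.2 SD | 63–78% | 43–64% |
| 0.3 SD | 32–57% | 11–33% |
| 0.48 SD (the size planned for pain, not EQ-5D) | 3–18% | under 1% to 3% |

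Adjustment makes straddling less common but does not remove it.

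**Step 5: what a straddling ratio looks like.** Illustration only: utility gain 0.03, SD 0.20, r = 0.6, 8-week timing (raw SE 0.0185), cost difference 800 with SE 600, both differences drawn as independent normals. The point ICER is about 46,200, and the 2.5th and 97.5th percentiles of the ratio are about −450,500 and 508,400. About 16% of draws are dominated and 8% dominant, and both give negative ratios.

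**Step 6: size at the level of the decision.** Assume gamma costs with mean $20,000 and shape 2, independent of QALYs. The SE of the cost difference is (20,000/√2) × √(2/72) ≈ $2,357. The SE of incremental net benefit is √(2,357² + (λ × SE of QALY difference)²).
- λ = $50,000: from 2,449 to 2,442 (0.3% lower) at the low end; from 2,548 to 2,418 (5%) at the high end.
- λ = $100,000: from 2,706 to 2,680 (1%) at the low end; from 3,049 to 2,594 (15%) at the high end.

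Cost variation dominates here, so the gain on net benefit is much smaller than on the denominator. It grows with larger λ or less variable costs.

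**The case against.** The strongest reply is that the same Aim 3 text largely handles this. Directly after the ICER it plans a net-benefit regression, which has no ratio problem, and the sentence on covariates in regression models can be read to cover it. On that reading the plan already contains an adjusted, ratio-free assessment of cost-effectiveness. That stands, and it is the main reason the point is minor. What it leaves open is the unstated λ, the unnamed baseline characteristics, and an ICER that is still computed from raw QALY means.

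It is also fair to say that no error has been shown. The covariate sentence concerns regression models and the ICER step is not one, so the text does not contradict itself. The precision argument in the power section was written for Aim 1, and carrying it over to the ICER is an efficiency preference.

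A reader might infer more than the documents support:
- That the ICER denominator is biased. Randomisation keeps it unbiased; the issues are precision and chance imbalance.
- That the bootstrap interval has wrong coverage, or is a percentile interval. The plan states no interval type, and no coverage failure was shown.
- That the ICER interval decides Aim 3. The plan sets no such rule.
- That the cost numerator should also come from a model with "gamma error distributions and log links for costs". The planned difference in mean costs is unbiased. The plan allows for productivity gains as well as costs, so zero or negative values are possible, and a gamma model may not suit them. In a simulation of that substitution, a wrong covariate form gave bias of up to 0.11 SE.

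**Conclusion.** The point holds as a minor, free improvement. The ICER denominator ignores a covariate that the trial collects and already plans to use elsewhere in Aim 3. The cost is an SE of the QALY difference that is larger than it need be (adjustment would lower it by about 4 to 44%) and exposure to chance baseline gaps worth 0.004 to 0.016 QALY per SE. The gain for incremental net benefit is about 0.3 to 15% of its SE at λ of $50,000 to $100,000, and nothing if the planned net-benefit regression already includes baseline EQ-5D. These ranges rest on assumed EQ-5D SD, correlations, visit weeks, costs and λ, and on independence of costs and QALYs; the documents give none of these. Whether the QALY difference will straddle zero cannot be known from the documents. The primary outcome is unaffected.

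**What to change.** Amend the Aim 3 text before the comparative analysis, so that the choice between raw and adjusted QALYs is not made with results in hand:

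1. Estimate incremental QALYs for the ICER by regressing QALY on group and baseline EQ-5D, in the full sample and again in each bootstrap resample. Leave the cost numerator as planned.
2. State that the planned net-benefit regression includes baseline EQ-5D and baseline resource use, and report incremental net benefit with its 95% CI over a stated range of λ.
3. If the bootstrap QALY differences straddle zero, show the replicates by quadrant of the cost-effectiveness plane, and do not present limits of the ratio as a range of cost per QALY.

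The cost is some SAP wording and a short piece of code. No new data are needed, since both baseline variables are already planned covariates. The downsides are a little more analysis work and possibly no single readable ICER interval to report.

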Social Cognitive Theory. mPCST-Community has been designed to specifically exploit four factors that, according to social cognitive theory,⁷⁴ strongly influence self-efficacy for pain control. First, mPCST-Community seeks to enhance patients' mastery of pain coping skills by allowing them to practice and receive feedback on skills in their own environment. For instance, after patients learn the pain coping skill of progressive muscle relaxation (PMR) at their first session, they will be encouraged to share their home experience with their therapist by sending a videotext of their environment and experience. The therapist will provide feedback and problem solve around any difficulties (e.g., barking dog) also through videotext. PMR is typically taught and practiced only in a small room setting at the medical center and patients are asked to imagine their home practice setting and describe potential issues/problems that might arise. Second, mPCST-Community will provide patients with multiple vicarious learning(i.e., modeling) experiences for each pain coping skill. Modeling of skills will take place by the therapist in session and through videos, through a character in a video clip, and through other patients' stories. Patients will be able to access the video clips and stories at any time via their smartphone; to increase the salience of vicarious learning, the content has been targeted to women with breast cancer. Third, patients will receive verbal encouragement from the therapist, personalized to the patients' home skills practice experience. For instance, when a patient learns the pain coping skill of activity/rest cycle they will discuss it with their therapist in the video-session and will then video themselves in the space in their home where they tend to overdo an activity (e.g., dishes, yard work) and describe their plan for not overdoing. The therapist will then provide encouragement about their plan. The therapist will be able to help the patient identify a rest location and problem solve around observed environmental obstacles. Finally, mPCST-Community provides opportunities for patients to receive feedback about any negative physiological or psychological initial reactions when practicing skills in their own environment. For example, if a patient feels increased pain or tension when practicing PMR in a certain chair or in a dimly lit room; problem solving can be used to alter environmental cues.

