- Describe the study, providing details regarding the study intervention (drug, device, physical procedures, manipulation of the subject or the subject's environment, etc.). Discuss justifications for placebo control, discontinuation or delay of standard therapies, and washout periods if applicable. Identify procedures, tests and interventions performed exclusively for research purposes or more frequently than standard of care. Include alternative therapies, concurrent therapies discontinued per protocol, risk benefit ratio, and use of tissue/specimens. Discuss monitoring during washout periods if applicable. Include brief description of follow-up, if any.

Research Plan. Women with breast cancer (N=190) will be randomly assigned with equal allocation to: 1) mPCST-Community or 2) mHealth-Education. Both conditions (mHealth-Ed) will involve four 50-minute individual sessions conducted over the course of 8 weeks with videoconferencing at the participant's community-based clinic or at the participant's home. Participants in mPCST-Community and mHealth-Ed will receive a smartphone to extend the intervention into their home environment. The study mobile application will provide participants in the mPCST-Community with: a mobile application that provides text and audio of intervention content tailored for low literacy, modeling video-clips, stories from other patients with pain, and other mPCST-Community materials (e.g., relaxation audio). The mPCST-Community participants will also enter daily pain, fatigue, and hassles levels and daily coping skills practice; this data will be used to send personalized messaging encouraging skills use. Innovative components of the mPCST-Community intervention include: new hybrid delivery modality (i.e., videoconferencing in community clinic, smartphone) to make such a protocol accessible to patients in medically underserved communities, adaptation for low-literacy patients, and use of personalized messaging. The therapist delivering the intervention will be at Duke University Medical Center and the participants will be at their community-based clinic. Participants may also choose to complete sessions in their home environment. mHealth-Ed participants will be given smartphones to access education session information, receive cancer education based messaging, and an education app. Participants will complete assessments at baseline, post-intervention, and at a 3- and 6-month post-intervention follow-up.

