3. Potential Risks. The primary risks of this study are those associated with confidentiality. There is some risk attendant to confidentiality of self-report data. Two password protected databases will be used for this study to ensure confidentiality. First, a tracking database will be used for recruitment and follow-up. This data will house information related to tracking the participants in the study, such as phone numbers and addresses. No medically sensitive or outcome data will be stored in this database. This database will also track nonparticipants (i.e., those who have declined participation) only to the barest minimum to ensure that they are not contacted again about participation. At the end of the study, all identifiable data of non-participants such as their names will be deleted. Tracking data on participants will be retained for the usual required period. Second, all study data will be stored in a separate password protected RedCap database without any personal identifiers. Data in this database will be derived from patients' direct input into the electronic patient reported outcomes system which is an onlinesurvey system; data entered into this system is stored on a secure server housed behind the DUMC firewall. Only a unique study identification number will link the electronic data to the study data file. The tracking data and study data will be stored in a file on a secure DUMC psychiatry server which can only be accessed by necessary members of the research team. Access to the Duke network requires a password protected, 128-bit encrypted virtual private network connection provided by Cisco systems.

There is also some risk of loss of confidentiality inherent to the use of video conferencing to conduct the study intervention sessions. To protect patient privacy, we will work with Duke's Institutional Review Board and Duke Medicine's Information Security Office (ISO) to implement the most up to date and secure videoconferencing option available at the time of study conception. The study mobile application may also present some risk of loss of confidentiality. Information input by participants into the mobile application is stored in a MySQL database. This is a standard security feature which allows the database to be kept separate from the web server to protect access to the database. In addition, the hard drive of the database machine will be encrypted, which will provide security in case the hard drive is physically compromised.

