
Data & Safety Monitoring

- Summarize safety concerns, and describe the methods to monitor research subjects and their data to ensure their safety, including who will monitor the data, and the frequency of such monitoring. If a data monitoring committee will be used, describe its operation, including stopping rules and frequency of review, and if it is independent of the sponsor (per 45 CFR 46.111(a) (6)).

This behavioral pain intervention trial carries minimal risk. All patients in the trial will continue their usual care during the course of trial, thus their doctors will provide monitoring of the patients' overall medical status. All research personnel who have direct contact with patients will be trained to observe and report any adverse event to the principal investigator. The principal investigator will report any adverse events to the institutional review board at Duke University within 48 hours. An adverse event is defined as any untoward medical occurrence during the clinical investigation that has a causal relationship to the study protocol. A serious adverse event is defined as any event which results in death, is immediately life threatening, results in persistent or significant disability/incapacity, patient hospitalization, or is serious for

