any other reason representing significant hazard. We will also appoint two data safety officers. One data safety officer will be a MD who is not associated with this study. The appointed MD officer will have experience with clinical research and trials and have a thorough understanding of adverse events. The other safety data officer will be a senior investigator who has technology expertise and will have an annual responsibility to evaluate our current mHealth system of assessment and intervention and identify any problems. All adverse events will be reported to Duke's IRB and the data safety officer in real time. All data will be stored on a secure server with multiple backups created regularly. All interactions with study participants will be under the direction of a Licensed Clinical Psychologist ([name] [PI]). Study investigators and staff for this trial will be taught to monitor for any signs that participants are experiencing high levels of physical or emotional distress that need to be addressed outside the context of this trial. If this is determined to be the case, the PI will work directly with the participant to move forward in a way that is in the best interest of the patient. No participant will be kept in the trial if they are experiencing increased extreme distress. [name] works directly with Cancer Patient Support and Care at Duke Cancer Institute as a practicing licensed clinical psychologist and as a supervisor to psychology trainees (i.e., advanced graduate students, clinical psychology interns); she is integrated into the psychosocial care program at the Cancer Center and has experience referring cancer patients who are distressed to appropriate psychosocial or psychiatric care within this large team of mental health professionals. She will use the same resources when making referrals for distress participants in this study.

Privacy, Data Storage & Confidentiality

- Complete the Privacy and Confidentiality section of the iRIS submission form.

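### The only stated route for adverse events into study reporting is passive staff observation; no common safety query is described for either arm at the post-intervention, 3-month or 6-month assessments

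*Combined protocol and SAP*

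**What the plan says.** **Detection.** Data & Safety Monitoring states: "All research personnel who have direct contact with patients will be trained to observe and report any adverse event to the principal investigator". Reported events then go to the IRB within 48 hours, and to the IRB and the data safety officer in real time. These timelines apply once an event is known. They do not say how it is found.

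**Definition and window.** "An adverse event is defined as any untoward medical occurrence during the clinical investigation that has a causal relationship to the study protocol". The window is the whole investigation, not only the session weeks. The definition of a serious event that follows includes hospitalisation.

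**Other safeguards.** Patients stay in usual care, "thus their doctors will provide monitoring of the patients' overall medical status". Also, "staff for this trial will be taught to monitor for any signs that participants are experiencing high levels of physical or emotional distress". Neither statement is limited to one arm or one period. Neither comes with a schedule or an instrument, and no reporting path from the treating doctors to the study is given.

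**Contact.** Design & Procedures says: "Both conditions (mHealth-Ed) will involve four 50-minute individual sessions conducted over the course of 8 weeks with videoconferencing". Aim 3 adds that the control arm was built to match contact time. The Social Cognitive Theory part of Background & Significance describes videotext exchanges about home practice for mPCST-Community: "The therapist will provide feedback and problem solve around any difficulties (e.g., barking dog) also through videotext". Design & Procedures adds daily symptom and practice entries for that arm. For mHealth-Ed it describes a smartphone, messaging and an education app.

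**Follow-up.** Both arms are assessed at baseline, post-intervention, 3 months and 6 months. Under Potential Risks, the study database is described thus: "Data in this database will be derived from patients' direct input into the electronic patient reported outcomes system".

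**Resource use.** Aim 3 will "test for differences between mPCST-Community and the Health-Edu conditions on medical resource use, medical costs and productivity costs". The opening project summary calls this resource use all-cause.

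**The concern.** Passive detection finds an event only when a staff member happens to be in contact with the patient and something is noticed or volunteered. In this trial that has two consequences.

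First, follow-up is thinly covered. The reporting window includes it, but nothing in the plan asks the patient about harms during it. An absence of late reports would then say little about whether late events occurred, in a trial that enrols stage I to IV disease.

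Second, the opportunity to detect an event may differ between arms. A therapist exchanging videotexts between sessions has chances to learn of a problem that have no described counterpart in the control arm. If anyone later set adverse events side by side by arm, an excess under mPCST-Community could reflect the extra exchanges and not the intervention.

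Meanwhile the trial collects resource-use data that could reveal some of the missing events, and nothing sends that information to the people responsible for safety.

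**Working it through.** The plan states no figure on this point, so there is none to reproduce. The check is a comparison of passages with some simple arithmetic.

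1. **Session contact** (Design & Procedures). Sessions x minutes = 4 x 50 = 200 minutes in each arm. Difference: 200 - 200 = 0.

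2. **Contact outside sessions.** mPCST-Community has therapist videotexts and daily app entries. No equivalent is described for mHealth-Ed. No videotext frequency is given, so the difference has a direction but no calculable size. The daily entries are said to drive personalised messages; the plan does not say that anyone reads them for safety.

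3. **Scheduled study points after the sessions** (Design & Procedures). Post-intervention, 3 months and 6 months: 3 in each arm.

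4. **Of those, points with a stated adverse-event query.** 0 of 3 in each arm. The documents neither state nor exclude staff contact at these points; they say only that patients enter the data themselves.

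5. **Share of post-baseline time after the sessions.** Share = follow-up weeks / (session weeks + follow-up weeks), assuming 6 months = 26 weeks.
   - Sessions spread over the full 8 weeks: 26 / (8 + 26) = 26/34 = 76%.
   - Sessions completed weekly in 4 weeks: 26 / (4 + 26) = 26/30 = 87%.

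   This is a share of time, not a share of events missed.

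6. **Aim 3 data against safety reporting.** Aim 3 compares patient-level resource use between arms. All-cause use would ordinarily include hospital stays, although the documents do not list the items. The serious-event definition names hospitalisation. No sentence in either section links the two. A hospital stay after session 4 could therefore be counted in the cost analysis without anyone judging whether it was related to the study.

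7. **Causality.** An event must be causally related to the protocol to count as adverse. That judgement can be made only after the event is known, so the causal definition does not remove the need to ask.

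**The case against.** The case on the other side is substantial.

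- **There are scheduled points after session 4.** This stands. A reader might infer that follow-up has no scheduled study point at all; the three assessments contradict that. What is missing is a safety question at them.
- **Contact is matched.** This stands for sessions. A reader might infer that mPCST-Community simply has more contact; the documents support only additional between-session exchange, of unstated frequency.
- **Other safeguards exist.** Treating doctors follow patients, staff watch for distress, and a physician not associated with the study serves as a safety officer. So it would be wrong to say that no safety monitoring takes place. But the doctors have no stated path to the study, distress monitoring has no timetable, and the officer sees only what is reported.
- **The outcomes themselves capture plausible harms.** Pain, fatigue, disability and distress are trial outcomes, and worsening on them is the likeliest harm of a coping-skills programme. This partly stands, but no rule sends a worsening score to a safety officer, and these outcomes do not cover hospitalisation.
- **No between-arm comparison of adverse events is planned.** Correct. Unequal detection matters only if such a summary is made. The gap in follow-up does not depend on it.
- **Most hospitalisations will be due to cancer or its treatment.** Likely. A reader might multiply a guessed hospitalisation rate by the 76% to 87% of time to count missed events. The documents give no rate, all-cause stays are not adverse events under the plan's causal definition, and an event outside the session weeks is not necessarily undetected.
- **The trial is described as minimal risk.** This limits the weight of the point, but a low expected rate of harm is no reason to leave most of the reporting window without a question.

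**Conclusion.** The point holds in a limited form. Followed as written, the plan relies on passive observation as its only stated route into safety reporting. It describes no identical scheduled query in the two arms, and it leaves hospitalisations in the Aim 3 data without a path to the safety officers. Events in the 6-month follow-up, 76% to 87% of post-baseline time, may go unseen. The videotexts and daily entries in mPCST-Community may make detection unequal; the size of that effect is unknown.

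This rests on three assumptions: 6 months is 26 weeks, sessions take between 4 and 8 weeks, and the Aim 3 resource use includes hospital stays. It also takes the documents' silence on a safety form to mean that none is planned. If one exists in study materials outside this protocol, citing it here would settle most of the point.

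No efficacy aim is affected. This is an inexpensive improvement to safety ascertainment, not a defect in the trial's main comparison.

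**What to change.** 1. Add the same few safety items (hospitalisation, new or worse symptoms, distress needing care) to the post-intervention, 3-month and 6-month assessments in both arms.
2. State that a hospitalisation reported there, or found in the Aim 3 resource-use data, is passed to the principal investigator and the MD safety officer for causality review. Leave the adverse-event definition and the reporting timelines as they are, so that only events judged related to the protocol become reportable adverse events.
3. Base any by-arm summary of adverse events on these common assessments. List events found through sessions or videotexts separately.
4. State whether staff are in contact with patients at the follow-up assessments, and who reads the safety responses when they arrive.

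**Cost.** A few questions in an existing online survey, an alert, and a named person to act on it. No new visits are needed. The main downside is more events to review, most of them unrelated to the study. The symptom and distress items will overlap in part with the outcome questionnaires.
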